5.7 Procedures for Monitoring Subject Compliance

The number of capsules of study product returned to the site will be counted and recorded on Visits 2 (Day 15), 3 (Day 29), 4 (Day 57), and 5 (Day 85). Note that at Visit 2, the study drug capsules will be counted to evaluate compliance, but the bottles will be returned to the subject for dosing until Visit 3.

5.8 Treatment Discontinuation and Subject Withdrawal

5.8.1 **Interruption of Dosing and Study Treatment Discontinuation**

Interruption of continued dosing in individual subjects may occur for safety reasons and at the discretion of the site investigator, if it is felt that interruption of dosing is in the best interest of the subject. Other than in urgent situations, it is recommended that the site investigator discuss the reasons for interruption of dosing with the Protocol Chairs and DAIT/NIAID prior to interruption. Multiple on-off periods of treatment with study drug are permitted, as necessary in the judgment of the investigator for safety purposes.

Study treatment will be discontinued permanently for any individual subject under the following conditions:

- 1. At any time during the study at the request of the subject or subject's guardian
- 2. If investigators or the DAIT/NIAID Medical Monitor determine(s) that the subject's health, safety, and/or well-being are threatened
- 3. Study treatment will be discontinued for any subject who experiences any of the following:
 - A severe flare by the SELENA SLEDAI Flare Index or a BILAG A in any domain except musculoskeletal
 - Starting a medication that is prohibited during the study (See Table 2 in Section 5.6, *Prohibited Medications*)
 - Increases in doses of methotrexate, mycophenolate, azathioprine, leflunomide, belimumab, cyclosporine, or tacrolimus above stable baseline doses
 - Any Grade 3 or higher AE or SAE that, in the opinion of the blinded site investigator, is at least "possibly related" to study product
 - Pregnancy. (See Section 7.6, *Pregnancy Reporting*)

Abrupt discontinuation of treatment with JBT-101 is not known to cause any harmful effects; therefore, study product will be stopped without tapering or adding additional treatments. All remaining study product will be returned to the study staff.

There will be no dose modification in this study, other than temporary or permanent discontinuation.

5.8.1.1 Procedures for Discontinuation of Protocol-Specified Treatment Requirements

Whenever possible, subjects who have been discontinued from study treatment should complete all scheduled study visits including all exams, procedures, assessments, and tests for the duration of the study. Furthermore, if discontinuation is due to safety concerns, subjects will be given appropriate care under medical supervision beyond the last scheduled study visit, if necessary, until the symptoms of any AE resolve or the subject's condition becomes stable. If the site Principal Investigator (PI) determines that completion of these visits is not clinically appropriate for the subject or if the subject or subject's guardian elects not to complete these visits, the subject will be withdrawn from the study per the guidelines in Section 5.8.2.1, *Procedures for Subject Withdrawal from the Study*.

5.8.2 **Subject Withdrawal from the Study**

When a subject is withdrawn from the study, protocol-specified treatment requirements are discontinued, and study-related visits, exams, procedures, assessments, tests and data collection are terminated. Individual subjects will be withdrawn from the study under the following conditions:

- The subject or subject's guardian withdraws consent
- If the subject elects to participate in any other sort of study or clinical trial (excluding observational registries or cohorts), the subject may be withdrawn at the discretion of the DAIT/NIAID
- Subject non-compliance with treatment regimens or failure to keep appointments

5.8.2.1 **Procedures for Subject Withdrawal from the Study**

All withdrawn subjects will have a follow-up visit after study product is discontinued for final safety monitoring. The timing of the Early Withdrawal Visit in this study is 28 ± 3 days after study product is discontinued. Assessments will be the same for subjects who withdraw before completing all dosing and those who complete all dosing. Subjects who withdraw consent will be asked to complete the Early Withdrawal Visit; however, they will not be required to complete the visit.

Subjects who are withdrawn due to pregnancy will be followed according to the procedures outlined in Section 6.1.9, *Pregnancies*.

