5.4.2 Management of Potential Risks to Study Product

Severe symptoms related to the potential risks of JBT-101 may necessitate stopping study drug. Stopping study drug is not a reason for withdrawal from the study, but a subject may be withdrawn at the discretion of the PI if deemed it is in the subject's best interest.

For subjects who experience potential CB1/CB2 mediated AEs (fatigue, dizziness, decreased concentration, feeling "weird", lightheadedness, asthenia, somnolence, GI disturbances such as nausea or vomiting, or dry mouth), treatment for symptoms should be prescribed as needed, and study treatment may be withheld at discretion of PI.

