7.3 Collection and Recording of Adverse Events

7.3.1 **Collection Period**

AEs of Grade 2 and above will be collected from time of signing of informed consent until the subject completes study participation, or until 30 days after he/she prematurely withdraws (without withdrawing consent), or is withdrawn from the study. See Section 7.4, *Grading and Attribution of Adverse Events* for grading criteria.

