8.2 Analysis Populations

8.2.1 Modified Intent-to-Treat Population

The modified Intent-to-Treat population (mITT) will consist of all randomized subjects who have received at least one dose of study product. The mITT population will be used for all efficacy analyses and will include subjects under the treatment to which they were randomized, regardless of compliance with assigned treatment.

8.2.2 **Per Protocol Population**

The per protocol population (PP) will consist of mITT subjects who:

- complete Visit 3 (Day 29), without missing more than 7 days of study product between Visit 1 (Day 1) through Visit 3 (Day 29).
- have ≥ 80% compliance with study drug administration from Visits 1- 5 (Days 1-85), as assessed by numbers of capsules of study product returned to the site, excluding periods off study drug when directed per protocol by the site investigator or treating physician)
- complete the study without protocol violations deemed likely to effect the efficacy outcomes of interest

A masked data review panel will evaluate deviations from the protocol including, for example, violations of entry criteria, departures from assigned treatment regimen, modifications of concurrent therapy, failure to complete study visits, or administration of study procedures outside the specified visit windows to determine if occurrence of these deviations should exclude subjects from the PP population.

The PP population will be used for secondary efficacy.

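### Section 5.8.2 makes non-compliance and missed appointments, with no threshold, mandatory grounds for ending data collection, at odds with the protocol's own follow-up policy

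*Protocol*

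**What the plan says.** Section 5.8.2 opens its list with "Individual subjects will be withdrawn from the study under the following conditions". The last condition is "Subject non-compliance with treatment regimens or failure to keep appointments". Only the co-enrollment condition is left to discretion; this one is mandatory as worded and has no threshold. On withdrawal, treatment requirements cease and "study-related visits, exams, procedures, assessments, tests and data collection are terminated".

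Other sections point the other way:

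- 5.8.1.1, for subjects taken off treatment: "Whenever possible, subjects who have been discontinued from study treatment should complete all scheduled study visits".
- 5.4.2: "Stopping study drug is not a reason for withdrawal from the study". Its exception is withdrawal by the investigator in the subject's best interest.
- 8.2.1: the mITT analysis "will include subjects under the treatment to which they were randomized, regardless of compliance with assigned treatment".
- 8.2.2: the per-protocol set requires at least 80% compliance and a masked panel reviews missed visits, so such subjects are expected to be in the data.
- 5.8.2.1: "All withdrawn subjects will have a follow-up visit after study product is discontinued for final safety monitoring".
- 7.3.1: adverse events are collected "until 30 days after he/she prematurely withdraws (without withdrawing consent), or is withdrawn from the study".

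Section 8.3.2.1 limits the primary analysis to pain scores up to the last dose and excludes those entered after treatment is discontinued.

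**The concern.** Read literally, a subject who stops drug altogether is kept on the visit schedule where possible, while a subject who takes part of the doses, or misses a visit, is removed. For the partly compliant subject, withdrawal itself ends treatment and so creates the cut-off that 8.3.2.1 then applies. On-treatment pain scores that the primary model would have used are never collected.

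Poor compliance can follow from tolerability (1.3.4 and 1.5.1 report dizziness and fatigue) or from lack of benefit. Removal may therefore differ by arm and be related to pain. Section 8.11 expects data to be missing at random and generally does not impute, so it is unwise for the protocol to create such gaps itself. With no threshold, sites may also apply the rule differently. Finally, these withdrawals end treatment and so count towards the 12% premature-discontinuation trigger for enlarging the sample in 8.1.

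**Working it through.** **1. Data lost.** The daily diary is used for Days 1 to 84. Withdrawal at Visit 3 (Day 29) loses Days 30 to 84: 84 − 29 = 55 scores, and 55/84 = 65%. Scheduled assessments at Visits 4, 5 and 6 also go. The Early Withdrawal Visit (5.8.2.1, 6.4.2.7) falls 28 ± 3 days after the last dose. If that was Day 29, the visit is at Day 57 ± 3, in Visit 4's slot, with joint counts, SELENA SLEDAI, BILAG 2004, Physician's Global Assessment and patient-reported outcomes. It measures the subject off drug and does not replace Visits 5 or 6.

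**2. The plan's power figure.** Inputs are the Table 5 pooled row (intercept variance 2.35, slope variance 0.00063, covariance −0.027, residual 0.49), Scenario 2 changes of 0, −0.25d, −d, −d with d = 1.6, 25 per arm and alpha 0.05. With Σ the covariance of the random effects and X the intercept-and-day matrix, one subject contributes information X'V⁻¹X, where V = XΣX' + 0.49·I. A non-central F for the 3 df contrast (83-day span, denominator df 4n − 4 = 96) gives 80.8%. Section 8.1 says power exceeds 80%, so the figure reproduces.

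**3. Precision.** Same model, assumed fractions withdrawn equally in all arms (the protocol gives no rate):

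| Withdrawn | Scores end Day 28 | Scores end Day 14 |
|---|---|---|
| 0% | 80.8% | 80.8% |
| 5% | 80.2% | 79.7% |
| 10% | 79.7% | 78.4% |
| 20% | 78.5% | 75.6% |

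The power loss is small.

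**4. Bias illustration.** Assume that 3 of 25 in an active arm (12%) are non-adherent with no benefit, the other 22 have the 1.6-point effect, and placebo is unaffected. If everyone is followed, the arm effect is (22/25) × 1.6 = 0.88 × 1.6 = 1.41.

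If the three contribute scores only up to Day L, let A be the information from a full record and B that from Days 1 to L. The generalized least squares estimate is (22A + 3B)⁻¹(22A·β₁ + 3B·β₀), where β₁ carries the 1.6-point decline over the span and β₀ no change:

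| Withdrawal day | Estimated effect | Minus 1.41 | Relative |
|---|---|---|---|
| 15 | 1.57 | 0.16 | 11% |
| 29 | 1.48 | 0.07 | 5% |
| 57 | 1.42 | 0.01 | about 1% |

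The ceiling, with no data at all from the three, is 1.6 − 1.41 = 0.19, or 14%.

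**The case against.** The best defense is that the primary endpoint is hardly touched. Section 8.3.2.1 already excludes scores after treatment stops, so for anyone who has given up the drug further diary entries would not enter the primary analysis. That stands, and it confines the primary-endpoint loss to partly compliant subjects still dosing.

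A reader might infer that 5.8.2 contradicts the mITT definition. It does not. Section 8.2.1 settles who is analysed and in which arm; a withdrawn subject who took one dose stays in as randomized, and 8.11 uses whatever data exist. What suffers is the purpose of an analysis that disregards compliance.

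A reader might also infer that all data collection stops. Section 6.4.2.7 requires procedures at the time of withdrawal and an Early Withdrawal Visit with efficacy measures, and 7.3.1 keeps adverse-event collection for 30 days. These soften the loss, though they make 5.8.2 inconsistent with its own subsection.

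The 14% ceiling is tempting as the size of the bias, but it treats non-adherers as deleted, whereas scores before withdrawal remain in the model. The 12% is the treatment-discontinuation figure in 8.1, not a non-compliance rate.

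Nor is missingness not at random established: withdrawal that depends only on arm and recorded pain is compatible with the 8.11 assumption.

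Lastly, 5.8.2 is the only explicit provision ending treatment for non-compliance or non-attendance, because the list in 5.8.1 has none. Visits also carry safety tests and the pregnancy test required before dispensing. Simply striking the condition would therefore change clinical management as well as follow-up.

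**Conclusion.** The inconsistency is real and worth correcting. As written, 5.8.2 makes an undefined degree of non-compliance, or missed appointments, a compulsory reason to end scheduled follow-up. That conflicts with the policy in 5.8.1.1 and 5.4.2, with what 8.2.2 presupposes, and with 5.8.2.1. It produces avoidable and possibly informative missing data, chiefly on-treatment pain scores of partial adherers and later visit-based secondary outcomes.

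The likely size is modest: about 0.07 points (5%) for withdrawal at Day 29, 0.16 at Day 15 and 0.01 at Day 57. These figures rest on 3 of 25 non-adherers, zero benefit in them, a 1.6-point effect in the rest, and the linear model with pooled Table 5 covariances. Zero benefit is severe for someone still taking part of the doses. On the other side, the planned quadratic model may borrow less from early scores; Table 5 gives no covariances for it, so that effect is not sized here.

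**What to change.** In 5.8.2, remove non-compliance and missed appointments as grounds for ending data collection. State that these subjects continue the IVRS diary and remaining visits on the 5.8.1.1 terms, that is, where possible and unless consent is withdrawn.

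Reconcile 5.8.2 with 5.8.1, 5.8.1.1, 5.8.2.1 and 5.4.2, keeping the end of data collection separate from the end of treatment. Whether and when study treatment stops for non-compliance or missed visits is for the sponsor to decide and state; this point takes no position on it.

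The cost is a short protocol amendment, and sites following a few more subjects on the existing schedule.

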5.8.3 Safety Stopping Guidance

In addition to the pre-scheduled data reviews and planned safety monitoring, the DSMB may be called upon for ad hoc reviews or emergency meetings. The DSMB will review any event that potentially impacts safety at the request of the protocol chair or DAIT/NIAID. The DSMB will have the discretion to recommend actions regarding study conduct and continuation as a consequence of any planned or unplanned monitoring activity.

In addition to the planned safety reviews, the DSMB will be informed of the following events as they occur:

- Any immediately life threatening event or death that occurs in the study that is at least possibly related to study intervention
- Two or more subjects with QT-prolongations defined as QTc prolongation > 500 msec total duration and > 60 msec from Visit 1 (Day 1) QTc interval prior to study drug administration

In addition, the following events will trigger both a comprehensive DSMB Emergency Safety Review and a temporary halt in enrollment:

- After the first 20 subjects are randomized, the occurrence of a Grade 3 or higher unexpected SAE in 10% or more of the study participants who have received study drug
- Two grade 3 or above AEs with the same or similar preferred terms associated with CB1 agonists deemed at least possibly-related to study drug.
- Determination of unexpected, significant, or unacceptable risks to subjects that contraindicate further dosing of additional subjects, in the opinion of the Protocol Chairs or DAIT
- Any new safety information about JBT-101 from other clinical trials that would pose significant or unacceptable risk to subjects

In the event of a temporary halt in enrollment, no new subjects will be consented or start on therapy with JBT-101 or placebo; and subjects already on JBT-101 or placebo will continue on therapy unless they are the focus of the DSMB review. Subjects in the screening phase of the study may continue to undergo minimal risk procedures (e.g., blood tests), but more than minimal risk procedures should be deferred. Randomization will not occur until the DSMB review is complete. The FDA will be notified of any halt in enrollment. After careful review of the data, the DSMB will make recommendations regarding study conduct and/or continuation.

6 ASSESSMENT OF SAFETY AND EFFICACY

6.1 Assessments of Eligibility and Safety

The following laboratory safety tests will be done at regularly scheduled intervals: hematology (CBCs with cell differential and platelet count); chemistry (complete metabolic panel including electrolytes, renal function, and liver function tests); urinalysis with microscopic examination; and pregnancy testing in women with childbearing potential.

Medical history, physical examination, and prior medications will be completed at Screening, for purposes of eligibility. Physical examination results, adverse events, and concomitant medications will be recorded as per Table 3, *Schedule of Events*.

Psychoactivity of JBT-101 will be assessed using the ARCI-M questionnaire at Visit 1 (Day 1) and follow-up visits per Table 3, *Schedule of Events*. Twelve-lead ECGs and QT/QTc intervals will be assessed at Screening and at Visit 1 (Day 1) and Visit 5 (Day 85). Both ARCI-M questionnaire and QT/QTc intervals will be assessed on Visit 1 (Day 1) prior to treatment and between 2.5 and 3.5 hours after the first dose of JBT-101, when plasma concentrations of JBT-101 should be about maximal.

Blood and urine laboratory safety tests, CRP, anti-DNA antibody tests, C3 levels, C4 levels, and urine protein/creatinine measurements will be done in central laboratories. A central reading center will be used to determine QT/QTc intervals.

6.1.1 Medical History and Use of Contraception

At Screening, a medical history will be performed and include subject demographics, history of SLE including current symptoms and past and present organ involvement, and current treatment for SLE. The medical history assessment will include concurrent illnesses, other current medications, past medical history, and review of systems. Child-bearing potential, last menstrual period and use of effective methods of contraception will be assessed for all women at Screening (See Appendix A: Reproductive Potential and Effective Methods of Contraception). Date of last menstrual period will be assessed for all women of childbearing potential at Visits 1 (Day 1) and follow-up visits per Table 3, *Schedule of Events*. Concurrent illnesses, current medications, and review of body systems will occur at Visits 1 (Day 1) and follow-up visits per Table 3, *Schedule of Adverse events* should be reported (See Section 7.4, *Grading and Attribution of Adverse Events*).

6.1.2 **Concomitant Medication and Treatment History**

A list of current prescription and over-the-counter medications, supplements, and treatments for SLE will be obtained. Assessment of eligibility should include a review of permitted and prohibited medications. Concomitant medications will be recorded on the concomitant medication eCRF from Screening through Visit 6 (Day 113). The medication, dose, frequency, route, start date, stop date, and indication will be captured.

6.1.3 **Physical Examination**

At Screening, a physical examination is performed to assist in determining the subject's eligibility for the study. Physical examinations also will be performed at Visits 1 (Day 1) and follow-up visits per Table 3, *Schedule of Events*. Physical examinations will include the following assessment: alertness and orientation, general appearance, skin, head, eyes, ears, nose, and throat, lungs, heart, peripheral pulses, abdomen, musculoskeletal examination including tender, swollen, and painful joints, reflexes and lymph nodes. Breast and genitourinary examinations are not required. The Visit 1 (Day 1) physical examination will be used as baseline.

6.1.4 Vital Signs, Height and Weight Measurements

Weight, systolic and diastolic BP, pulse (P), respiratory rate (R), and temperature will be recorded on Screening and all Visits. Weight will be measured with outerwear, such as coats and jackets, and footwear removed. The systolic and diastolic BP will be measured with the patient seated and will be recorded after at least 5 minutes of rest. The same arm will be used for the measurement throughout the study. Pulse will also be measured with the subject seated at rest for at least 5 minutes. Body temperature will be measured on the skin or in the

mouth. These vital sign measurements should be obtained prior to taking samples for the laboratory testing at the applicable study visits. Standing height is to be measured at Visit 1 (Day 1) with footwear removed.

6.1.5 **Disease Flares for Safety Assessment**

The original lupus instruments to assess disease flares included an evaluation of proteinuria based on the protein:creatinine ratio derived from a 24-hour urine. For this study, the protein:creatinine ratio will typically be derived from the spot urine assessment although a 24-hour urine may be used if the investigator believes it is indicated.

6.1.5.1 SELENA SLEDAI (28 day assessment)

The SELENA SLEDAI is a validated measure of global disease activity in SLE and was modified from the original SLEDAI for the SELENA clinical trial in 1997. The original SLEDAI was developed in 1992; it includes both subjective reports from patients and objective findings from physicians and laboratory data [111]. The SELENA SLEDAI modification of the original SLEDAI changed some of the item definitions in order to clarify attribution and change in disease activity. These included changes to definitions of seizure activity, strokes, serositis, visual disturbances and proteinuria [109, 112].

The SELENA SLEDAI is a one page assessment that contains 24 items covering 9 organs systems and items are scored as either present or absent. Each item is assigned a weighted score. Two systems can score a maximum of 8 points each, 2 systems can score a maximum of 4 points each, 3 systems can score a maximum of 2 points each, and 2 systems can score a maximum of 1 point each. Scores range from 0–105 points. A score of 6 is considered clinically important and may affect the decision to treat. The original SLEDAI captured disease activity within the 10 days prior to assessment; however, this time period was extended to include the previous 30 days [113, 114].

The SLEDAI does not record improving or worsening, and does not include severity within an organ system. The sensitivity to change is less for the SLEDAI than other commonly used outcome measures in SLE [115].

